**2.9. DURATION OF THE STUDY**

Based on time needed for multiple centers, the time required for IRB approval, the randomization of patients for enrollment and completed follow-up, the duration of this study is expected to be 12 years.

**3. SELECTION AND WITHDRAWAL OF SUBJECTS**

- A. Process: Patients will be screened according to the inclusion / exclusion criteria detailed in Section 3.1 and 3.2. If a patient consents to participate but is found to be ineligible prior to commencement of first bony cut intraoperatively, this will be documented on the screening log.
- B. Screen Failures: A screen failure can occur up to and prior to the first bony cut of the surgical technique. The ACL should be assessed intraoperatively to screen out any patients without sufficient soft tissue to participate, and if insufficient documented on the screening log as a screen failure. In the event that the patient receives a non randomized study device AFTER the first bony cut has commenced due to surgeon discretion, this patient is considered a randomization failure, but will still be followed in the study. Any patient consented that is a screen failure will not count towards the sample size, and will be replaced.

**3.1. INCLUSION CRITERIA**

Subjects will be considered for inclusion in this trial if they satisfy the following study criteria\* and FDA cleared indications for use:

- A. Cemented application of components\*
- B. Bilateral subjects randomized by knee\*
- C. Patients with pre-existing contralateral knee surgery\*
- D. Painful and disabled knee joint resulting from osteoarthritis, rheumatoid arthritis or traumatic arthritis where one or more compartments are involved.
- E. Correction of varus, valgus, or posttraumatic deformity
- F. Sufficient soft tissue surrounding the knee, including the Anterior Cruciate Ligament.

**3.2. EXCLUSION CRITERIA**

Subjects should be excluded from this trial if they satisfy any of the following study criteria\* and contraindications for the device:

- A. Cementless application of components\*
- B. BMI  $\geq 40 \text{ kg/m}^2$ \*
- C. Use of Anterior Stabilized Bearings\*
- D. Patients with severe pre-operative varus or valgus deformity  $\geq 15$  degrees\*
- E. Correction or revision of previous joint replacement procedure on index knee\*
- F. Infection
- G. Sepsis
- H. Osteomyelitis

Relative contraindications include:

[figure not shown]
- I. Uncooperative patient or patient with neurologic disorders who is incapable of following directions
- J. Osteoporosis
- K. Metabolic disorders which may impair bone formation,
- L. Osteomalacia
- M. Distant foci of infections which may spread to the implant site
- N. Rapid joint destruction, marked bone loss or bone resorption apparent on roentgenogram
- O. Vascular insufficiency, muscular atrophy, neuromuscular disease
- P. Incomplete or deficient soft tissue surrounding the knee, including the anterior cruciate ligament.\*

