**2.2. STUDY GROUPS/TREATMENTS****A. Arm 1 (Control) : Vanguard CR Total Knee System**

Patients who receive the cemented Vanguard CR femur with Vanguard CR Bearing based on meeting indications for use, and inclusion / exclusion criteria described in the protocol.

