**2.4. RANDOMIZATION**

Patients will be randomized using a 1:1 blocked randomization scheme. Bilateral patients should be randomized by knee. Randomization will occur by enrolling the patient into Joint Assist and assigning an operative date. At that point the electronic database will assign the treatment group for the patient. The patient will be blinded from treatment until surgery has occurred.

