**E. Clinical Assessments**

1. **Intra-operative Data:**
  - a. An operative record will be completed to record details of each operative procedure and of the used implants. Operative room procedure time, tourniquet time, components used, and Intraoperative complications will be recorded on the operative record.

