**B. Randomization Failures:**

1. A randomization failure is a patient who has been randomized but does not receive the intended randomized treatment. These patients' randomization assignments will not be re-used, and randomization should continue with the next patient being screened and consented.
  - a. If the randomization failure occurs prior to the first bony cut, the patient is not considered "enrolled" and this should be documented on the screening log as a "screen failure" with the reason and rationale described (e.g. insufficient ACL). No further data should be collected on this patient. Screen failures do not count towards the sample size and will be replaced.
  - b. If the randomization failure occurs after the surgery has commenced with the first bony cut, but due to the surgeon's discretion, the randomized treatment will not be the best treatment for the patient, the surgeon should implant according to their discretion and standard of care at the center. This patient counts toward the overall sample size and will not be replaced. Data should be collected on these patients per protocol.

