**14.4. INFORMED CONSENT**

- A. All patients require informed consent due to the research interventions and data collection required of this study. Subjects (or the subject's legally authorized representative) will be provided with an informed consent in order to give ample opportunity to review the consent and ask questions. The signed informed consent will be obtained before any study procedures begin. If the subject agrees to participate in the study, the

subject/representative must sign the informed consent form. The Investigator or his/her qualified designee must also sign the informed consent form. A copy of the informed consent form should be given to the subject/representative. All subjects who meet all of the entry criteria will be considered for inclusion in this trial. Any subject meeting any of the exclusion criteria will be excluded from the trial.

- B. The informed consent form must be approved by the institution's IEC/IRB.
- C. Subjects will be informed of new information learned during the study, which may affect the subject's decision to continue participation in the study.
- D. An enrollment case report form will document for the sponsor that the center has obtained the required signed informed consent form. Fully signed informed consent forms (or copies) are to be maintained in the study file by all centers, and must be available for verification by monitors or inspectors.

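### Exclusions 3.2 C and 3.2 A can be met at surgery, after randomization, and the protocol gives conflicting rules on whether such knees stay in the trial

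*Combined protocol and SAP*

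**What the plan says.** Timing. Section 2.4 fixes the arm before the operation: "Randomization will occur by enrolling the patient into Joint Assist and assigning an operative date". Section 3.2 C then excludes on "Use of Anterior Stabilized Bearings", and 3.2 A on cementless application. Neither is limited to what is planned or known pre-operatively, whereas criterion D in the same list is expressly pre-operative. What was implanted is documented at surgery (2.7 E): "An operative record will be completed to record details of each operative procedure and of the used implants".

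Arms. Section 2.2 A describes the control arm as "Patients who receive the cemented Vanguard CR femur with Vanguard CR Bearing". Both arms are defined as cemented.

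Rules for a knee that departs from its assignment:
- Section 3 B: "A screen failure can occur up to and prior to the first bony cut of the surgical technique". After that point, a patient given a device other than the one assigned is a randomization failure and is still followed.
- Section 3.3 B.1.b, on a failure after the first cut: "This patient counts toward the overall sample size and will not be replaced". Data are to be collected.
- Section 14.4 A: "Any subject meeting any of the exclusion criteria will be excluded from the trial". No time limit is attached.
- Section 15 I: the definition of withdrawal includes a randomization failure arising once surgery has begun. The withdrawal criteria in 3.4 D do not.

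Analysis. Sections 8.1 and 8.2 specify a two-sided Pearson chi-square test on two proportions. Neither says which knees enter it, or in which arm a randomization failure is counted.

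**The concern.** The bearing used and the fixation used are facts of the operation, not baseline characteristics. As worded, 3.2 C and 3.2 A let a knee become ineligible after its arm is known to the surgical team. If such a knee is then dropped, the comparison no longer rests on everyone randomized. The knees lost may differ between arms in number and in prognosis.

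The retention rule in section 3 would prevent this, but two other statements in the same document point to removal, and no analysis set settles the matter. Sites could handle identical knees differently, and the choice of who is analyzed could be made after outcomes are known.

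**Working it through.** **1. One knee under each rule.** Take a knee randomized to CR that receives an anterior stabilized bearing after the first bony cut.

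| Section | Consequence |
|---|---|
| 2.2 A | Control is defined with the CR bearing, so the assigned treatment as defined was not received |
| 3 B | Too late to be a screen failure |
| 3.3 B.1.b | Randomization failure: counted, not replaced, data collected |
| 3.2 C with 14.4 A, read literally | Excluded |
| 15 I | Withdrawn |
| 8.1, 8.2 | Silent on inclusion and on arm |

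A knee in either arm given cementless components after the cut meets the same conflict through 3.2 A, because both arms are defined as cemented. One uncertainty remains within section 3. Sections 3 B and 3.3 A speak of a study device or component that was not the randomized one, and the plan does not say whether an excluded bearing counts as such. The definition opening 3.3 B is broader (the intended treatment was not received) and does cover it.

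**2. The plan's own figure.** Inputs from 8.1: proportions 0.66 and 0.83, two-sided alpha 0.05, power 90%. Group 1 is taken as CR and group 2 as XP, since the table does not label them. With pooled variance under the null:

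n = [1.960·√(2·0.745·0.255) + 1.2816·√(0.66·0.34 + 0.83·0.17)]² / 0.17² = (1.208 + 0.775)² / 0.0289 ≈ 136.1, so 137 per arm.

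Power at 137 per arm is 0.902. 137/0.90 = 152.2, so 153 per arm and 306 in total. The stated figures reproduce and are not in dispute.

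**3. Illustration of removal.** The documents give neither the share of knees affected nor their outcome, so both are assumed. Let a share r of the 137 evaluable CR knees be removed, with feeling-normal rate q among them. Then:

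remaining CR rate = (0.66 − r·q)/(1 − r), and power = Φ[(d − 1.96·SE₀)/SE₁],

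where d is the remaining difference, SE₀ the pooled and SE₁ the unpooled standard error, with 137(1 − r) CR and 137 XP knees.

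| r | q | CR rate | Difference (points) | Power |
|---|---|---|---|---|
| 0 | – | 0.660 | 17.0 | 0.902 |
| 5% | 0.66 | 0.660 | 17.0 | 0.895 |
| 5% | 0.50 | 0.668 | 16.2 | 0.866 |
| 5% | 0.30 | 0.679 | 15.1 | 0.822 |
| 10% | 0.66 | 0.660 | 17.0 | 0.887 |
| 10% | 0.50 | 0.678 | 15.2 | 0.818 |
| 10% | 0.30 | 0.700 | 13.0 | 0.700 |

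Worked case, r = 10%, q = 0.30: (0.66 − 0.03)/0.90 = 0.700; d = 0.13; SE₀ = 0.0524; SE₁ = 0.0523; Φ[(0.13 − 0.1026)/0.0523] = Φ(0.523) = 0.700.

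With no true difference (both arms 0.66), the two-sided type I error over the rows with q of 0.30 or 0.50 runs from 0.052 to 0.105.

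**4. Direction.** If XP knees were removed instead, the difference would grow. At r = 5%, q = 0.50: (0.83 − 0.025)/0.95 = 0.847, difference 18.7 points. At r = 10%, q = 0.30: (0.83 − 0.03)/0.90 = 0.889, difference 22.9 points. The sign therefore depends on which arm loses knees, which the documents do not say.

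**The case against.** The best defense is that section 3 governs selection and already gives the right answer. Eligibility is checked at pre-operative screening (2.7 B), screen failure ends at the first bony cut, and later departures are kept and followed. On this view 3.2 C and 3.2 A describe planned configurations that fall outside the study. That fits the section 1.2 aim of limiting variables and the parallel inclusion criterion of cemented application. The 14.4 A sentence sits in the consent section beside a statement about entry, and reads naturally as an entry rule.

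Much of this stands. Removal is one reading of conflicting passages, not a settled rule. But the planned-use reading is nowhere stated, and the consent-section argument does not reach section 15 I, which conflicts with 3.3 B.1.b directly.

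A reader might go further and infer that these exclusions remove knees according to how the assigned implant performed, that they drop the least stable CR knees, or that they select on the outcome. The documents do not support this. No passage says why an anterior stabilized bearing would be used, how often, or in which arm. Section 1.2 contrasts the systems' constraint only in general terms. Knee stability appears in the study summary and in 1.3 but is not named among the 2.5 endpoints, and a bearing chosen during surgery is not a postoperative stability result.

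**Conclusion.** The concern holds as a conflict between rules, not as a demonstrated bias. Two exclusion criteria can be met after randomization. Section 3 retains a knee that meets one after the first cut, 14.4 A read literally excludes it, and 15 I withdraws it. With no analysis set defined, nothing prevents such knees from being left out of the primary test.

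The size and direction of any effect cannot be derived from the documents. Under the assumed loss of 5–10% of CR knees with a feeling-normal rate of 0.30–0.50, the 17-point difference falls to about 16 to 13 points and power from 0.90 to between 0.87 and 0.70. If the removed knees share their arm's rate, there is no bias and only a small loss of power (0.89 at 10%). The true frequency may be well below these values. The case for acting is that the ambiguity is cheap to remove.

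**What to change.** Reconcile 3.2, 14.4 A and 15 I with 3 B and 3.3 B:
- Limit 3.2 C and 3.2 A to planned use known before randomization. Deleting 3.2 C outright goes further than needed, because it would also admit knees for which such a bearing is planned.
- Limit the 14.4 A sentence to criteria assessed before the first bony cut.
- Take post-cut randomization failure out of the 15 I withdrawal definition, so that it agrees with 3.3 B.1.b and 3.4 D.
- State in 3.3 B.1.b and 8.2 that a knee receiving such a bearing, or cementless components, after the first bony cut is recorded on the operative form, stays enrolled, is followed for all endpoints and is analyzed in its randomized arm.

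The cost is protocol wording only, since the components used are already recorded at surgery. The downside is that a few knees with a non-study configuration stay in the comparison. None of this takes a position on which bearing or fixation a surgeon should use.

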**3.3. SUBJECT ENROLLMENT****A. Definition of Study Enrollment :**

1. A patient is considered enrolled after they have been preoperatively screened for eligibility, consented to participate, and after surgeon's first intraoperative bony cut:
  - a. Received a randomized study component.
  - b. Received a non-randomized study component (randomization failure) due to surgeon discretion and standard of care at the local center.
2. Enrolled patients will be documented on the Enrollment form.

**B. Randomization Failures:**

1. A randomization failure is a patient who has been randomized but does not receive the intended randomized treatment. These patients' randomization assignments will not be re-used, and randomization should continue with the next patient being screened and consented.
  - a. If the randomization failure occurs prior to the first bony cut, the patient is not considered "enrolled" and this should be documented on the screening log as a "screen failure" with the reason and rationale described (e.g. insufficient ACL). No further data should be collected on this patient. Screen failures do not count towards the sample size and will be replaced.
  - b. If the randomization failure occurs after the surgery has commenced with the first bony cut, but due to the surgeon's discretion, the randomized treatment will not be the best treatment for the patient, the surgeon should implant according to their discretion and standard of care at the center. This patient counts toward the overall sample size and will not be replaced. Data should be collected on these patients per protocol.

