**1.2. DEVICE DESIGN AND DESCRIPTION**

Both knee systems included in this trial have been 510(k) cleared by the United States Food and Drug Administration (FDA). Both systems have the same indications for use (see section 3.1). The main difference between these total knee systems is that the Vanguard XP system requires a functional Anterior Cruciate Ligament (ACL), and the Vanguard CR system requires the anterior cruciate ligament to be sacrificed. Therefore the Vanguard XP Knee System is constrained by natural soft tissue, and the Vanguard CR is constrained by soft tissue and device design. Both systems allow the surgeon to retain the posterior cruciate ligament. Biomet knee joint replacement components include femoral, tibial, and patellar components. Components are available in a variety of designs and size ranges intended for both primary and revision applications. Specialty components are available including; femoral stems, femoral augments, tibial stems, tibial augments, tibial cement plugs and tibial screws.

For purposes of this study, in order to reduce variables with randomization, only patients receiving a primary total knee with a functional ACL will be enrolled. If the ACL is deemed not functional (either preoperatively or intraoperatively), the patients will be treated according to local standard of care and will not be enrolled into this study. A chart comparing the devices is provided:

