**14.5. SUBJECT CONFIDENTIALITY**

- A. General Responsibilities:
  - 1. The Sponsor and centers will maintain the confidentiality of the identity of subjects enrolled in the study and the information contained in their study records. The Sponsor will also instruct the study investigators in the importance of maintaining the confidentiality of study records. The records will be made available as required for review by governing regulatory agency such as FDA and a reviewing IEC/IRB, however to the extent possible, the subject's identity will not be disclosed.
- B. Electronic Data Capture
  - 1. Once the site enters a patient into Joint Assist, the database will assign that patient an ID number. It is the responsibility of the investigator to maintain a list of patient identification and Joint Assist ID numbers throughout the course of the study. By assigning patients a unique ID number, their identity is protected in Joint Assist, the online database. The database is restricted, allowing a doctor to only view and enter data from his own patients. User authentication is required to view research data. The data is transmitted to a centralized database through a secured (SSL) channel on the Internet. Data in transit is in 128-bit encryption. The access to the centralized database is limited to those who are responsible for maintaining the database.

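### The arm is assigned before the last ACL check, nothing described conceals it from the surgeon, and randomized knees that fail the check leave the trial without outcome data

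*Combined protocol and SAP*

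**What the plan says.** Randomization (section 2.4) takes place when the patient is entered in Joint Assist and given an operative date: "At that point the electronic database will assign the treatment group for the patient". The only blinding described there is the patient's: "The patient will be blinded from treatment until surgery has occurred".

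Eligibility can still be decided after that. Section 3 B states "A screen failure can occur up to and prior to the first bony cut of the surgical technique", and that "The ACL should be assessed intraoperatively to screen out any patients without sufficient soft tissue to participate". Section 1.2 allows the judgement at either time: "If the ACL is deemed not functional (either preoperatively or intraoperatively), the patients will be treated according to local standard of care", and such patients are not enrolled. No section gives an objective threshold for a sufficient or functional ACL.

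Section 3.3 B covers patients who have already been randomized. If the failure comes before the first bony cut, the patient goes on the screening log as a screen failure with the reason, and then: "No further data should be collected on this patient. Screen failures do not count towards the sample size and will be replaced". Failures after the cut are treated differently: they count toward the sample size and data collection continues.

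The devices differ on exactly this feature (section 1.2): "the Vanguard XP system requires a functional Anterior Cruciate Ligament (ACL), and the Vanguard CR system requires the anterior cruciate ligament to be sacrificed".

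**The concern.** A knee dropped between assignment and the first cut is a post-randomization exclusion, whatever the log calls it. Such exclusions are harmless when they are made without knowledge of the arm. Here the plan does not secure that, and the exclusion turns on a judgement whose practical consequence depends on the arm. In a borderline knee, ACL quality decides whether XP can be implanted, while in a CR case the ligament is removed anyway. A surgeon who knew the arm could, without intending to, pass such a knee for CR and fail it for XP.

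The primary comparison, the percentage of patients whose knee feels normal, would then be made between groups selected differently. The bias would favour XP if the knees dropped from that arm would have done worse, and would work against XP if they would have done better. Because follow-up stops for dropped knees, their post-operative outcomes could not be recovered later to test this.

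**Working it through.** **1. The plan's own figure.** Section 8.1 gives proportions 0.66 and 0.83, two-sided alpha 0.05 and 90% power. With the mean proportion 0.745:

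n = [1.960·√(2·0.745·0.255) + 1.282·√(0.66·0.34 + 0.83·0.17)]² / 0.17² = 136.05, so 137 per arm.

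Power at 137 is 0.902. Allowing for 10% loss, 137/0.9 = 152.2, so 153 per arm and 306 in all. The sample size reproduces; the concern is not about arithmetic.

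**2. The order of events.**

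| Step | Section | Who knows the arm, per the plan |
|---|---|---|
| Operative date set, arm assigned | 2.4 | Patient blinded; surgeon not addressed |
| ACL judged, possibly in theatre | 1.2, 3 B | Surgeon not addressed |
| Failure before the cut: logged, no further data, replaced | 3.3 B | Log asks for the reason, not the arm |
| First bony cut: patient counts as enrolled | 3.3 A | Enrollment form records the assignment (2.7 B) |

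**3. What uneven exclusion could do.** The documents give no late-failure rate and no outcome for dropped knees. The two inputs below are therefore assumptions: f, the share of knees dropped, and g, the amount by which their rate of feeling normal falls below that of retained knees. Assume also no true device effect, 66% normal among retained knees, and 137 analysed per arm. Section 8.1 does not say which device has 0.66; it serves here as the common rate.

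With d = pX − pC, p̄ their mean, s0 = √(2p̄(1−p̄)/137) and s1 = √([pX(1−pX) + pC(1−pC)]/137), the rejection rate is Φ((d − 1.96·s0)/s1) + Φ((−d − 1.96·s0)/s1).

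- One-sided exclusion (XP only): pX = 0.66 and pC = 0.66 − f·g.
- Partial imbalance (10% of knees borderline, all dropped in XP, half in CR): pX = 0.66 and pC = [0.90·0.66 + 0.05·(0.66 − g)]/0.95.

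| Case | pC | Shift toward XP, points | Type I error |
|---|---|---|---|
| One-sided, f = 5%, g = 20 points | 0.650 | 1.0 | 5.3% |
| One-sided, f = 10%, g = 17 points | 0.643 | 1.7 | 6.0% |
| One-sided, f = 10%, g = 30 points | 0.630 | 3.0 | 8.1% |
| Partial, g = 20 points | 0.6495 | 1.1 | 5.4% |
| Partial, g = 30 points | 0.6442 | 1.6 | 5.9% |
| Any f, g = 0 | 0.660 | 0 | 5.0% |

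First row in full: s0 = 0.05744, s1 = 0.05743, and Φ(−1.786) + Φ(−2.134) = 0.0371 + 0.0164 = 0.0535. Full binomial enumeration agrees with the normal approximation to within 0.1 percentage point in these cases. If dropped knees would have done better, the shift runs against XP.

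**4. Would a count by arm reveal it?** Suppose 153 knees are retained per arm. Dropping 5% from XP and none from CR gives about 8/161 against 0/153, Fisher p = 0.007. Dropping 10% and 5% gives 17/170 against 8/161, p = 0.098. With true rates of 10% and 5%, p < 0.05 would be reached only about 38% of the time. A count would tend to show a one-sided pattern but could miss a partial one.

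**The case against.** **The rule is deliberate and the same in both arms.** Section 1.2 restricts the trial to functional-ACL knees to limit variability, and sections 3.1 F and 3.2 P apply to both devices. This stands. The rule is not at fault; the gap is that nothing ensures it is applied without knowledge of the arm.

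**Nobody says the surgeon sees the arm.** This also stands. Section 14.5 says "The database is restricted, allowing a doctor to only view and enter data from his own patients", which does not settle whether the assignment is among the data shown. A reader might infer that the surgeon knows the arm at the ACL check, or that the result will be tilted toward XP. The documents support neither inference. They show only that no concealment step is described.

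**The exclusions can be traced.** Largely true. Assignment happens inside Joint Assist (2.4), assignments are not re-used (3.3 B), each patient has an ID (14.5), and entered data are kept under an audit trail (10.2, 10.3). A reader might infer that uneven exclusion could never be checked, but a dropped knee's assignment should still be there and a by-arm count is feasible. What is missing is an instruction to make that count. The lost post-operative outcomes are a separate matter and would not be recoverable.

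**The effect is small.** In most of the illustrated cases it is. Fully one-sided exclusion is an extreme pattern under a common rule, and partial imbalance keeps the error below 6%. One cannot add that preoperative screening will leave few late failures, because no section gives a rate.

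**Conclusion.** The concern holds as a design weakness, not as a demonstrated bias. The order of steps is explicit, and confidence is high for that alone. Bias would need three things that the documents neither show nor rule out: an appreciable late exclusion rate, uneven use of the rule by arm, and a different prognosis in the knees dropped. Its presence, size and direction are therefore unknown. Over the assumed range the effect on type I error runs from negligible to modest. Severity is modest: the exposure touches the primary comparison and can be removed or monitored cheaply.

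**What to change.** **Preferred.** In sections 2.4 and 3.3, state that Joint Assist releases each knee's assignment only after the surgeon has recorded the ACL as sufficient, and before the first bony cut. This removes knowledge of the arm from the ACL judgement and leaves the eligibility rule and the 153 per arm unchanged. It costs an amendment, a change to when the system shows the assignment, and having both implant sets on hand for each case.

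**If assignment must stay pre-operative.** Record the assigned arm beside the reason on the screening log, and report pre-cut exclusions by arm with reasons and baseline scores. State that a partial imbalance could go undetected. This costs one field and one table.

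**Optional.** Replace the section 3.3 B instruction to stop data collection with PROMS by phone or mail, which section 2.6 already permits, for dropped knees whose patients still consent. Use these data only in a sensitivity analysis by assigned arm. The primary analysis stays in functional-ACL knees. The sensitivity analysis answers a diluted question, since dropped knees may not have received the assigned device. If 5%, 10% or 20% fail equally in both arms and 66% of them feel normal, the 17-point contrast becomes 17·(1 − f) = 16.2, 15.3 or 13.6 points. With 137/(1 − f), about 144, 152 or 171 per arm, power falls from 90% to about 88%, 86% or 81%, in that analysis only. The added cost is the amendment, the consent wording and the follow-up of knees now dropped.
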